### 5.3 Evaluation Method

#### 5.3.1 Evaluation of Efficacy

##### 5.3.1.1 Primary Endpoint

###### (1) Wound Volume Reduction Rate (unit: %)

**Define:** wound volume change over 14 days or until deemed ready for closure by investigator (whichever occurred first).

**Formula:** wound volume reduction rate = (wound volume before initial study treatment – wound volume after study treatment 14 days or deemed ready for closure before 14 days) ÷ wound volume before initial study treatment × 100%.

**Measurement:** 3D Wound Imaging System, digital photos and three-dimensional photographs will be taken of the wound (without dressing) by assigned staff for all subjects.

Three-dimensional wound images will be captured for randomization visit, dressing change visit (s), and end of treatment visit using a specialized imaging system. Imaging guidelines, equipment, and supplies will be provided to the investigational sites by KCI. The 3D images collected from each site will be aggregated into a single database. The aggregated images will be analyzed /measured by the independent assessor. The independent assessor will determine and plot the wound perimeter, the clean, healthy viable tissue, and other tissue types for each image. The imaging software will be used to calculate wound length, width, depth, surface area, and wound volume. The values of these parameters/assessments will be used for calculations of the primary endpoint and the secondary endpoints. The 3D wound images should not be used to guide patient treatment.

**Evaluation time point:** Day of Randomization (Day 0), Dressing Change Visit (s), and End of Treatment Visit.

**Statistical method:** the difference of wound volume reduction rate between investigational group and control group will be evaluated to determine whether the primary endpoint of the investigational group is non-inferior to that of control group.

**Rationale:** please see Section 5.1.2.5.

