### **5.3.1.2 Secondary Endpoints**

#### **(1) Time to Completion of Wound Bed Preparation (unit: day)**

**Define:** duration from the randomization until target wound ready for closure by secondary intervention judged by investigator.

**Evaluation time point:** Day of Randomization (Day 0) and End of Treatment Visit

**Measurement:** the date deemed ready for closure by secondary intervention - the date of the randomization + 1.

**Statistical method:** the difference between investigational group and control group will be assessed.

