15.2.2. TIME TO COMPLETION OF WOUND BED PREPARATION (UNIT: DAY)

Define: Duration from the randomization until target wound ready for closure by secondary intervention judged by the investigator.

Evaluation time point: Day of Randomization (Day 0) and End of Treatment Visit.

Measurement: the date deemed ready for closure by secondary intervention - the date of the randomization + 1.

Statistical method: the difference between investigational group and control group will be assessed by Kaplan-Meier method and log rank test, and with covariate adjustment using the Cox proportional hazard regression and Wald Chi-Square.

Censor data define: .

The duration of treatment for a patient is considered right-censored if it meets one of the below conditions:

- Patient completed the study but the completion category was “The treatment duration up to 14 Days”, and the subjects’ target wound not ready for closure before end of treatment visit. Patient’s will be censored on day of end of treatment visit.
- Patient prematurely withdraws from the study and the subjects’ target wound not ready for closure before end of treatment visit, patients will be censored on the date of their last 3D wound imaging assessment.
- Subjects with no post-baseline 3D imaging wound measurements assessments will be censored on the day of randomization (i.e. Day 0).

Here, duration of treatment for a patient is defined as the date of the last wound measurements assessments minus the date of randomization plus one.

The Kaplan-Meier analysis of the time to completion of wound bed preparation will be performed, the Kaplan-Meier plot will be presented. The Cox proportional hazard regression with covariates from primary endpoints will be used to estimate the hazard ratios for effect of treatment factor.

The results of the log-rank test for the comparison of investigational group and control groups will be expressed by a Chi-square statistic and P-value, The results of cox proportional hazard regression will be present by HR statistic and P value, the P-value <0.05 will be considered as statistically significant.

An example of SAS code for cox proportion regression model is provided:

```
Proc phreg;
Class treat(ref=control) center(ref=sitel1) woundtype(ref=1);
Model time*completion of wound bed preparation(yes) =treat center treat*center woundtype
/risklimits;
Run;
```

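### SAP 15.2.2 censors at Day 0 any subject without a post-baseline 3D image, even one with a recorded readiness date, and leaves the status of a wound first judged ready at the day-14 visit to an undefined category choice

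*SAP*

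**What the plan says.** Both documents define the endpoint in the same way. Protocol 5.3.1.2 (1) has "duration from the randomization until target wound ready for closure by secondary intervention judged by investigator", and SAP 15.2.2 times the event as "the date deemed ready for closure by secondary intervention - the date of the randomization + 1". No image enters the definition or the formula. Protocol 5.3.1.1 adds that "The 3D wound images should not be used to guide patient treatment".

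SAP 15.2.2 then lists three censoring conditions, introduced by "The duration of treatment for a patient is considered right-censored if it meets one of the below conditions":

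1. A subject for whom "Patient completed the study but the completion category was" 14-day duration, and with "target wound not ready for closure before end of treatment visit", is censored at the end of treatment visit.
2. A subject who withdraws early, with the same not-ready clause, is censored at the last 3D image.
3. "Subjects with no post-baseline 3D imaging wound measurements assessments will be censored on the day of randomization (i.e. Day 0".

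The analysis uses the FAS (SAP 15.2). The end of treatment visit is held either when the wound is judged ready or at 14 days, plus or minus one (Protocol 5.5.1, note 1, and 5.5.2.4).

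**The concern.** The third condition has no not-ready clause. Because any one condition is sufficient, it takes precedence over a readiness date that the investigator has recorded, and so makes an investigator-judged outcome depend on whether an image was taken. Missing images are foreseeable: SAP 6.1 lists a missing end-of-treatment volume as a reason for exclusion from the PPS. In this analysis the subject stays in the FAS but the event disappears.

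The first condition has a narrower problem. Its clause about readiness before the end of treatment visit does not separate ready from unready wounds, because that visit may itself be the occasion on which readiness is declared. What decides is the completion category. Two identical wounds, both first judged ready at the day-14 visit, can be an event in one subject and a censored time in another, depending on which box was ticked. Investigators know the treatment arm (Protocol 5.1.2.4).

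The event indicator feeds the Kaplan-Meier curve, the log-rank test and the Cox hazard ratio.

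**Working it through.** **Logic.** The three conditions, applied literally as an any-one-applies rule, give the following. Time is the readiness or censoring date minus the randomization date, plus 1.

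| Subject | Endpoint definition | SAP censoring list |
|---|---|---|
| Ready day 6, category ready, image present | event at 7 | event at 7 |
| Ready day 6, category ready, no post-baseline image | event at 7 | censored at Day 0 (condition 3) |
| First ready at day-14 visit, category ready, image present | event at 15 | event at 15 |
| First ready at day-14 visit, category 14-day duration, image present | event at 15 | censored at 15 (condition 1) |
| Not ready at day 14 | censored | censored (condition 1) |
| Withdrawn, not ready, image present | censored | censored at last image (condition 2) |

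Rows 2 and 4 are the defects. Row 2 follows from the text without further condition. Row 4 depends on the recorded category. A time censored at Day 0 precedes every possible event time (the formula gives at least 1), so the subject is never in a risk set and is in effect removed. SAP 15.2.1, which leaves missing times as missing, does not cover row 2, because there the readiness date is known.

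**Scale of condition 3.** The documents give no image-loss rate. Protocol 5.2.5 expects at least two dressing changes, and imaging is scheduled at each change and at end of treatment, so at least two post-baseline occasions would have to be missed. Assume 5% to 10% lost per occasion, independent losses, only two occasions for every subject, and every subject ready. With 85 per arm:

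- 85 × 0.05² = 0.2
- 85 × 0.10² = 0.85

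That is under one event per arm. If losses cluster within a subject or site, independence fails. Should 1% to 10% of subjects be ready with no post-baseline image at all, 170 × 0.01 to 170 × 0.10 = 1.7 to 17 events would go. The schedule makes the upper end unlikely.

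**Scale of condition 1 (upper bound).** Inputs: medians of 5 and 6 days, from the earlier post-marketing study in Protocol 3.1.3.1 and assumed to apply here, with 8 days added as a slower case; dressing changes every 48 to 72 hours (Protocol 5.5.3), so a last change at day L = 12 or 11. Assume exponential times, S(t) = 0.5^(t/median), and that every wound becoming ready after L is given the 14-day category. The share affected is S(L) − S(14); the share of events is that divided by 1 − S(14).

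| Median | L | S(L) − S(14) | of 170 | share of events | ready by day 14: true / reported |
|---|---|---|---|---|---|
| 5 | 12 | 0.046 | 7.8 | 5.4% | 0.856 / 0.811 |
| 5 | 11 | 0.074 | 12.6 | 8.6% | 0.856 / 0.782 |
| 6 | 12 | 0.052 | 8.8 | 6.4% | 0.802 / 0.750 |
| 6 | 11 | 0.082 | 14.0 | 10.3% | 0.802 / 0.719 |
| 8 | 12 | 0.056 | 9.6 | 8.0% | 0.703 / 0.646 |
| 8 | 11 | 0.088 | 15.0 | 12.6% | 0.703 / 0.614 |

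The median time is unchanged in every row, because it falls before day 11.

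**The case against.** The best defence is that condition 3 was meant only as a fallback for condition 2: censor an unready withdrawal at the last image, or at Day 0 if there is none. That is probably the intent, and a careful programmer might code it so. It is not what the text says: the list is governed by an any-one-condition rule, and the qualifier in the first two conditions is absent from the third.

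A reader might infer that every wound first judged ready at day 14 is censored. The documents do not support that. Condition 1 also needs the 14-day category, and both documents recognise readiness as a separate way of completing the study (Protocol 6.3; SAP 6.1). A wound categorised as ready is an event. The gap is that neither document says which category applies when both are true.

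A reader might also infer that the fastest responders are the ones most exposed, through having only one post-baseline image. The expected minimum of two dressing changes, with imaging at each, does not support this. Nor does an unreliable image necessarily trigger condition 3: SAP 6.1 distinguishes missing measures from unreliable ones.

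Nothing in the documents shows that losses would differ between arms; photographs are taken without the dressing. Nor do they say that the FAS was chosen to protect this endpoint from image problems.

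**Conclusion.** Wrong as written, for a secondary endpoint. Condition 3 gives the wrong status to any subject with a readiness date and no post-baseline image, contrary to the endpoint definition in the same section. Condition 1 may do the same to a wound first judged ready at the day-14 visit, depending on a category choice that is not defined.

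The frequency of either is unknown. For condition 3 it is probably low, and below one event per arm under the independence assumption. For condition 1, 8 to 15 of 170 subjects is a ceiling that rests on exponential times, borrowed medians and every such wound being categorised as 14-day duration; the true number could be zero. Neither a direction of bias nor an imbalance between arms can be claimed. The primary analysis of wound volume in the PPS does not use this event indicator, so its conclusion is unaffected.

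**What to change.** Add one rule to SAP 15.2.2: a subject with a recorded readiness date up to and including the end of treatment visit is an event on that date, whatever images exist and whichever completion category is recorded; the three censoring conditions apply only to subjects with no readiness date. This supplies the missing qualifier in condition 3 and makes the category question irrelevant, so the individual conditions need no rewording.

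The cost is one sentence and a matching line in the derivation of the event flag. The readiness date is already required by the endpoint formula, so no new data are needed. If the database is already locked, Protocol 6.6 asks for the change to be recorded in the statistical analysis report and the clinical study report; it would then be useful to state how many subjects per arm change status.

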### **5.5.2.2 Day of Randomization (Day 0)**

The following data will be collected:

- (1) Physical exam.
- (2) Wound clinical assessments

Wound depth, Edges, necrotic tissue type and amount, granulation tissue, undermining, exudate type and exudate amount will be evaluated.

For subjects who present with multiple wounds suitable for the trial, the wound with the greatest volume will be randomized.

- (3) Definitive surgical debridement (if applicable).
- (4) Digital/3D wound imaging

Digital photos and three-dimensional photographs will be taken of the wound (without dressing) for all subjects, and target wound length, width, depth, surface area and volume will be measured and reported.

When a wound extends over a convex/curved surface, such as a limb, the imaging will be taken so that each part of the wound is photographed (max. 2 photos) in a way that the photographed surface is as flat as possible in relation to the camera lens.

- (5) Evaluation of inclusion/exclusion criteria again.
- (6) Randomization

Subjects who continue to meet all inclusion and no exclusion criteria will be randomized in a 1:1 ratio stratified by wounds surface area (<15cm^2, 15-30cm^2, and > 30cm^2) to be treated with either investigational group [V.A.C. VERAFLTM Dressing Kit with ULTATM Therapy Unit (instillation) ] or control group [Negative pressure wound drainage material with Wall suction (without instillation)].

- (7) Administer assigned NPWT treatment

Date, time, condition and settings of NPWT treatment need to be recorded.

(8) Concomitant medications

All medications the subject is taking during the study.

(9) Collect and assess AEs/SAEs.

(10) Device deficiencies.

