### **Secondary and safety endpoints**

For other continuous secondary endpoints, the same analysis procedure will be conducted as above. In addition, Kaplan-Meier and log rank test will be performed for time to completion of wound bed preparation. An analysis of covariance (ANCOVA) model on mean change in wound area reduction rate as dependent variables with treatment group as fixed factors, site, treatment-by-site interaction (present only if interaction effect is significant) and wound size as covariate will be performed. The difference between the two treatment groups and 95% CI will be reported. The Wilcoxon rank-sum test and Wilcoxon signed rank test will be performed for wound clinical assessments.

In addition, all efficacy and safety endpoints will be summarized descriptively for subjects in each treatment group and overall. The continuous data will be summarized by number of subjects, mean, standard deviation (SD), median, minimum and maximum. The categorical data will be summarized by frequency counts along with associated percentages.

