4.1. GENERAL DESCRIPTION

This is a prospective, multicenter, randomized (1:1), open-label, parallel controlled, non-inferiority trial evaluating the efficacy and safety of V.A.C. VERAFL™ Dressing Kit versus Negative Pressure Wound Drainage Material (Guangdong Shuangling Pharmaceuticals Co., Ltd.) for wound bed preparation in open wounds with extensive soft tissue damage. This is a pre-marketing trial of V.A.C. VERAFL™ Dressing Kit in China for National Medical Products Administration (NMPA) registration. It is anticipated that the primary efficacy endpoint (wound volume reduction rate) of investigational group is non-inferior to that of control group. Approximately 140 subjects who meet the eligibility criteria will be randomized to the investigational group or control group at the ratio 1:1.

Debridement is not permitted during study treatment. Therefore, subjects will only be enrolled following definitive surgical debridement (if serial debridements performed) of the target wound. The target wound for each subject in both groups will be treated for up to 14 days or until deemed ready for closure by the investigator (whichever occurs first). Following study treatment, the wound may be treated with any standard therapy selected by the physician, and then accepted secondary intervention for wound closure according to the wound bed preparation situation. The planned study

period consists of the following visits: Screening (Day -3 to 0), Day of randomization (Day0), Dressing change visit(s), End of treatment visit. The following data in both groups will be recorded and collected: wound volume reduction rate, time to completion of wound bed preparation, wound area reduction rate, incidence of AEs / SAEs and device deficiencies. The efficacy and safety of V.A.C. VERAFL™ Dressing Kit in treating open wounds that have extensive soft tissue damage will be evaluated according to the above data.

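### The log-rank test of time to completion of wound bed preparation ignores the wound-area randomisation strata, so it is valid but somewhat conservative, and the SAP does not say whether it or the area-adjusted Cox test decides

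*SAP*

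**What the plan says.** Protocol 5.5.2.2 states that eligible subjects "will be randomized in a 1:1 ratio stratified by wounds surface area", with levels <15, 15-30 and >30 cm². No other stratification factor is named.

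For this endpoint, the first listed among the secondary endpoints, Protocol 6.5.1 (Secondary and safety endpoints) states: "Kaplan-Meier and log rank test will be performed for time to completion of wound bed preparation". No strata are mentioned.

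SAP 15.2.2 keeps the log-rank test, again without strata, and adds a model. The group difference "will be assessed by Kaplan-Meier method and log rank test, and with covariate adjustment using the Cox proportional hazard regression and Wald Chi-Square". On reporting: "The results of the log-rank test for the comparison of investigational group and control groups will be expressed by a Chi-square statistic and P-value". On the model: "The Cox proportional hazard regression with covariates from primary endpoints will be used to estimate the hazard ratios for effect of treatment factor". The primary-endpoint covariates in SAP 15.1.3 include wound area with the same three cut-points as the randomisation strata.

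SAP 15.2.2 judges p-values against 0.05, and SAP 7.5 makes tests two-sided by default. SAP 15.2 assigns this endpoint to the FAS. Neither document gives a power, event count or hazard ratio for it, or says which of the two p-values decides.

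**The concern.** Stratified allocation balances area across the arms, so the real sampling variation of the treatment comparison no longer contains chance imbalance in area. A pooled log-rank test still uses a variance that allows for it. If larger wounds take longer to become ready, the test rejects less often than its nominal level under the null. Pooling unlike strata also dilutes the apparent hazard ratio, which costs further power.

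What is at stake is interpretation of a secondary endpoint. With a moderate or strong area effect, the log-rank p-value could exceed 0.05 while the adjusted Cox p-value falls below it. Choosing between them after database lock would be open to challenge.

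**Working it through.** **Plan's own figure.** There is none for this endpoint. The stated 128 evaluable subjects belong to the primary endpoint. They reproduce: margin 20%, SD 40%, one-sided 0.025, noncentral t gives 64 per arm with power 0.8015. That says nothing about the log-rank test.

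**Statistics compared.** With U = observed minus expected events in one arm and V = its hypergeometric variance:

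- unstratified: Z = U/√V, with all subjects in one risk set
- stratified: Z = ΣU_g/√(ΣV_g), summed over the three area strata g
- Cox: Wald test of treatment, with area as a three-level factor

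**From the documents.** 1:1 allocation stratified by area at three levels; follow-up to day 14, then censored if not ready; two-sided 0.05. The control median of 6 days in the middle stratum is loosely anchored on the earlier post-marketing study in Protocol 3.1.3.1 (medians 6 and 5 days).

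**Assumed.** N = 160; permuted blocks of 4; exponential times rounded up to whole days; 10% random dropout; treatment hazard ratio 1.0 or 1.6; stratum shares of one third each or 10/30/60%; hazard ratio h between adjacent strata, so stratum hazards are h : 1 : 1/h. Centre effects are omitted.

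**Type I error** (6,000 runs; standard error √(0.05×0.95/6000) = 0.003):

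| h | Unstratified, equal | Stratified, equal | Unstratified, 10/30/60 | Stratified, 10/30/60 |
|---|---|---|---|---|
| 1 | 0.051 | 0.051 | 0.052 | 0.053 |
| 1.5 | 0.043 | 0.052 | 0.046 | 0.052 |
| 2 | 0.031 | 0.055 | 0.041 | 0.055 |
| 3 | 0.014 | 0.051 | 0.024 | 0.053 |

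**Power at treatment hazard ratio 1.6** (6,000 runs for h = 1.25 to 2; 2,000 for h = 3 and for all Cox figures):

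| Shares | h | Unstratified | Stratified | Loss (points) | Cox, area-adjusted |
|---|---|---|---|---|---|
| Equal | 1.25 | 0.758 | 0.764 | 0.6 | 0.759 |
| Equal | 1.5 | 0.717 | 0.759 | 4.2 | 0.755 |
| Equal | 2 | 0.615 | 0.752 | 13.7 | 0.746 |
| Equal | 3 | 0.41 | 0.72 | about 30 | 0.725 |
| 10/30/60 | 1.25 | 0.749 | 0.750 | 0.1 | 0.758 |
| 10/30/60 | 1.5 | 0.711 | 0.730 | 1.9 | 0.728 |
| 10/30/60 | 2 | 0.627 | 0.700 | 7.3 | 0.698 |

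There is no power figure for 10/30/60 at h = 3. In the Cox null runs (2,500, equal strata) size was 0.056 at h = 1.5 and 0.054 at h = 2.

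**Cost of stratifying when area has no effect (h = 1).** In 2,000 runs, unstratified against stratified power was 0.764 against 0.754 (equal shares) and 0.765 against 0.766 (10/30/60): at most about 1 point.

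**Second simulation.** With 170 subjects, equal strata, alternating allocation within strata and 1,500 runs, unstratified against stratified power was 81% vs 81% (no area effect), 75% vs 79% (stratum hazards 1.5/1/0.67), 65% vs 78% (2/1/0.5) and 44% vs 76% (3/1/0.33). The pattern is the same.

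**The Cox code as printed.** It keeps treat*center with a reference centre, so the treatment coefficient is the effect at that centre alone. By Schoenfeld's formula, power = Φ(√(d/4)·ln HR − 1.96). With an assumed d = 130 events in all:

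- whole trial: √32.5 × 0.470 − 1.96 = 0.72, power 0.76
- one of 3 equal centres (d = 43.3): 1.55 − 1.96 = −0.41, power 0.34
- one of 5 equal centres (d = 26): 1.20 − 1.96 = −0.76, power 0.22

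The number of centres is not given in the text reviewed. The code also puts the value yes where PROC PHREG expects the censoring value.

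**The case against.** The strongest reply is that the plan already contains an area-adjusted test. The sentence that names the log-rank also names a Cox Wald test, with covariates that include the three area levels. With equal strata at h = 2 it reaches 0.746, against 0.752 for a stratified log-rank. The treat*center term appears only in example code, and the primary model from which the covariates come drops a non-significant interaction. Protocol 6.5.1 can also be read as making the log-rank an addition to the ANCOVA used for continuous secondary endpoints. An unstratified log-rank beside a pooled Kaplan-Meier plot, followed by an adjusted model, is a coherent plan.

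Most of this stands. A reader might infer that the endpoint has no test using the stratification factor; SAP 15.2.2 shows otherwise. A reader might also infer that power is lost whenever area predicts readiness; for a weak effect the loss is within simulation error. The large losses need a fourfold (h = 2) or ninefold (h = 3) hazard range across strata, which nothing in the documents supports. The treatment hazard ratio of 1.6 is also only an assumption: the earlier study in Protocol 3.1.3.1 found no significant difference in time to readiness (p = 0.7105).

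What the reply leaves open is the deciding test. Both p-values are judged against 0.05 with no precedence. The log-rank is the only one of these two tests named in both documents. The Cox model appears only in the SAP, whose Section 2 records no change from the protocol. As coded, the Cox test is not a safe substitute.

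**Conclusion.** The point holds as a modest improvement to a secondary analysis. The log-rank test as specified is valid, somewhat conservative, and loses power when area is materially prognostic. At a treatment hazard ratio of 1.6 the loss is under 1 point at an adjacent-stratum hazard ratio of 1.25, about 2 to 4 points at 1.5 and about 7 to 14 points at 2, depending on stratum shares. These figures depend on an area effect, treatment effect and stratum shares that the documents do not give.

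The documents do not support reading this as a source of false positive claims, because the error runs the other way. Nor does it threaten the trial's main conclusion: the primary ANCOVA already includes area, and no power is claimed for this endpoint. The missing rule for which p-value decides is a gap whatever the size of the area effect.

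**What to change.** In SAP 15.2.2 and Protocol 6.5.1:

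1. Specify a log-rank test stratified by the wound-area stratum used at randomisation (<15, 15-30, >30 cm²), and name it as the deciding test for this endpoint at two-sided 5%.
2. Report the area-adjusted Cox model for the hazard ratio and its confidence interval. Remove treat*center from the example code and correct the censoring value.
3. Keep the unstratified log-rank beside the Kaplan-Meier plot as supportive only.

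Stratifying alone is not enough, since it would leave the stratified log-rank and Cox p-values without a stated order; item 1 must name the decider.

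The cost is one strata specification and a few sentences, with no new data and at most about 1 point of power if area turns out not to matter. Protocol 6.6 allows a change of method before data lock to be recorded in the SAP, so SAP Section 2 should carry the entry. It should be settled before database lock.

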### **3.1.3.1 Summary of Animal, in Vitro Studies and Clinical Trials**

While there is broad acceptance and a large body of evidence that supports NPWTi-d (with V.A.C. VERAFLDTM Dressing Kit) as an important tool in aiding wound healing. Most evidence include animal studies, expert opinion, case reports, case series and involving prospective treatment groups compared with control.

In 2012, Anthony et al, compared continuous and periodic wound instillation in conjunction with negative pressure wound therapy using an agar-based model. Continuous instillation at a rate of 30 cc/hour with negative pressure showed isolated exposure of instillation fluid to wound beds in agar wound models with and without undermining and tunneling. In contrast, periodic instillation illustrated uniform exposure of the additive to the entire wound bed including undermined and tunnel areas, with increased staining with each instillation cycle. These findings suggest that periodic instillation facilitates more uniform exposure throughout the wound, including tunnels and undermining, to instillation solutions, thereby providing therapy consistent with the

clinician-ordered treatment.

In 2013, Lessing et al, found that a greater reduction in wound area and perimeter in NPWTi-d wounds compared to all NPWT wounds ( $P < .05$ ) by 3D images Analysis on porcine excisional wounds.

In 2011, a post marketing study using VAC. VERAFLTM Dressing in operatively debrided wounds, the results showed that there was no statistically significant difference in the time to wound deemed ready or closure or coverage between NPWTi-d (n=71) and NPWT(n=66) subjects (mean 6.8 vs 6.3 days, median 6 vs 5 days, respectively;  $p = 0.7105$ ) in the Per-Protocol Population (NCT01867580).

In 2013, Brinkert et al, collected 131 patients treated with V.A.C. VERAFLTM Dressing. Mean duration of NPWTi-d was 12~19 days. 98% of the cases, the wounds were closed after debridement and following the use of NPWTi-d.

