Additional analyses will include summary statistics of the number of events and censored values, median time of duration as well as its 95% confidence interval will also be presented. Listings will be presented and sorted by treatment group, subject id.

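### SAP 15.2.2: the example PROC PHREG code treats readiness for closure as censored, the reverse of the section's own censoring rules

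*SAP*

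**What the plan says.** SAP 15.2.2 defines the endpoint as "Duration from the randomization until target wound ready for closure by secondary intervention judged by the investigator". It then introduces the censoring rules with "The duration of treatment for a patient is considered right-censored if it meets one of the below conditions" and lists three groups: subjects who reach the 14-day limit, subjects who withdraw early (for both, the condition is "target wound not ready for closure before end of treatment visit"), and subjects with no imaging after baseline. Readiness is therefore the event, and everyone else is censored.

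The section plans Kaplan-Meier, a log-rank test, and a Cox model that gives the covariate-adjusted hazard ratio, with p<0.05 called significant. Only the Cox model comes with code, introduced by "An example of SAS code for cox proportion regression model is provided". Its MODEL line is "Model time*completion of wound bed preparation(yes) =treat center treat*center woundtype".

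After the code the section adds: "Additional analyses will include summary statistics of the number of events and censored values".

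**The concern.** The PROC PHREG form is `MODEL time*status(list)`, where the list holds the censored values. With `(yes)` after the completion variable, every wound that became ready is censored, and every subject whom the prose censors becomes an event. One section thus gives two opposite instructions for one analysis.

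Nothing else in the two documents settles the conflict. There is no status-flag definition and no Kaplan-Meier or log-rank code to compare with. The only precedence rule, in SAP Section 8, puts the output templates above the SAP, and the templates are not in these documents.

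Time to completion is a named secondary objective (Protocol 4.2, SAP 3.2), and the Cox model is the only covariate-adjusted time-to-event analysis of it. A reversed fit would run without an error message once the variable name was tidied. It would print a plausible hazard ratio for ending treatment not ready or withdrawing. Since readiness is a good outcome, a ratio above 1 would be read as faster preparation in the investigational arm, when it would really mean more failures or withdrawals there.

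**Working it through.** **1. Prose and code side by side**

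| Subject | Censoring rules in the text | Code as printed |
|---|---|---|
| Judged ready for closure | event | censored |
| 14-day limit reached, not ready | censored at end-of-treatment visit | event |
| Withdrew, not ready | censored at last 3D imaging | event |
| No post-baseline imaging | censored at day 0 | event |

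The reversal follows from the syntax alone. The plan states no event count, hazard ratio or power for this endpoint, so there is no figure of its own to reproduce. The rest of the working shows the consequence.

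**2. Hand calculation without withdrawal**

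Under the printed coding, all events then fall together on the last day. For each arm (1 investigational, 0 control), let n be the number at risk on that day and d the number still not ready at its end. With Breslow ties (the PHREG default) the score equation is

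d1 = (d1 + d0) × n1θ / (n1θ + n0), which gives θ = (d1/n1) / (d0/n0).

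If readiness times are exponential with control median m days and true hazard ratio h, then d0/n0 = 2^(−1/m) and d1/n1 = 2^(−h/m), so θ = 2^(−(h−1)/m).

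- m = 5: h = 0.67, 1.5, 2.0 give 2^0.066 = 1.05, 2^−0.1 = 0.93, 2^−0.2 = 0.87.
- m = 8: the same values give 1.03, 0.96, 0.92.

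The printed coding therefore returns a value near 1 whatever the true effect, tilted slightly the wrong way. Any withdrawals move it towards the ratio of the arms' withdrawal rates.

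**3. Simulation with withdrawal**

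Inputs:
- 85 per arm (Protocol 6.1.1).
- Treatment ends at day 14; scenarios A and B were also run with ±1 day (Protocol 5.5.1).
- Times in whole days, plus 1 (SAP 15.2.2).
- Control median 5 days, from the conventional NPWT arm of the earlier study in Protocol 3.1.3.1 ("mean 6.8 vs 6.3 days, median 6 vs 5 days", instillation arm first), or 8 days (assumption).
- Withdrawal levels: all assumptions.
- Exponential times, Breslow ties, treatment as the only covariate. Scenarios A to C used 1,000 trials each.

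The table gives median hazard ratios. Percentages are the share of trials with p<0.05. A dash means that only the printed coding is reported.

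| Scenario | True HR | Correct coding | As printed |
|---|---|---|---|
| A. 2% per day withdraw, both arms | 0.67 | 0.68–0.69 | 1.02–1.04 |
| A | 1.5 | 1.44–1.47 | 0.95–0.97 |
| A | 2.0 | 1.88–1.95 | 0.89–0.95 |
| B. 15% of each arm withdrawn by day 14 | 0.67 | – | 0.89–0.96 |
| B | 1.5 | – | 1.08–1.22 |
| B | 2.0 | – | 1.24–1.54 |
| C. 15% control, 35% investigational withdrawn | 1.0 | 0.97–0.98 (4%) | 1.76–2.24 (71–85%) |
| C with arms swapped | 1.0 | – | 0.45–0.57 (72–83%) |
| D. 2% v 3% per day | 1.0 | – | 1.18–1.27 (2–8%) |
| E. 2% v 4% per day | 1.0 | – | 1.39–1.55 (18–19%) |

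In A, the chance of p<0.05 falls from 45–98% with correct coding to 3% or less as printed. In B the ratio is attenuated rather than flipped: the arm that becomes ready sooner spends less time at risk, so the same 15% withdrawn means a higher daily withdrawal rate there.

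**4. Check under other assumptions**

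A separate simulation used 400 trials per setting and control medians of 6 or 10 days. In it, 5% or 15% of subjects were given a withdrawal time, which counted only if they were not already ready.

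- True 1.5: 1.44–1.48 with correct coding, 0.91–0.97 as printed.
- True 2.0: 1.87–1.95 with correct coding, 0.90–0.94 as printed.
- p<0.05: 52–61% and 96–99% with correct coding, at most 0.8% as printed.

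At m = 10 the formula in step 2 gives 2^−0.05 = 0.966 and 2^−0.1 = 0.933; the simulated values were 0.967–0.968 and 0.935.

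**The case against.** The strongest reply is that this is pseudo-code. The status name contains spaces, no dataset is named, and the SAP's other examples are equally rough (a misspelt METHOD option in Section 16, two class variables run together in 15.1.3). A programmer must write the status coding afresh, with three correct censoring rules just above the example, and `(yes)` may have been meant to name the event. An error would also show: the section already requires counts of events and censored values, and PHREG prints its own. All of this stands, and it limits the weight of the point. It does not remove it, because a natural rewrite of the line keeps `(yes)` and the plan does not require the two counts to be compared.

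The reach is narrow, which also stands. The protocol names Kaplan-Meier and log-rank for this endpoint ("In addition, Kaplan-Meier and log rank test will be performed for time to completion of wound bed preparation"). The preceding sentence there could be read as applying the ANCOVA too, but neither reading involves the Cox code.

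The simulated sizes are open to challenge. Scenario C is a large imbalance with no support in the documents: the 25% drop-out in Protocol 6.1.3 is overall and covers every exclusion from the primary analysis. Scenarios D and E show the milder case, where the direction holds but false significance is much rarer. The fits omit center, its interaction and wound size, and use withdrawal dates rather than the last imaging date. The 5-day median comes from another study's per-protocol population. With that median the exponential makes 1 − 2^(−4/5) = 43% ready by day 4, which sits uneasily with at least two dressing changes 48–72 hours apart (Protocol 5.2.5 and 5.5.3). The ranges are therefore illustrative. The reversal itself does not depend on them.

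**Conclusion.** The concern holds. The example code in SAP 15.2.2 contradicts the censoring rules of its own section, and neither document corrects it. The harm is conditional on the status coding being carried over. In that case the adjusted hazard ratio stays near 1 when both arms withdraw at the same daily rate, even for a true hazard ratio of 2.0. When withdrawal is unequal, the ratio favors the arm with more withdrawals: 1.18–1.27 at 2% v 3% per day, and 1.76–2.24 at 15% v 35% withdrawn, with no true effect in either case. These sizes rest on assumed withdrawal levels, exponential times and an unadjusted model.

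The damage is confined to one adjusted hazard ratio and its p-value for a secondary endpoint. The primary non-inferiority conclusion, the Kaplan-Meier estimates and the log-rank test are unaffected. It should be fixed before programming, and it does not threaten the trial's main result.

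**What to change.** In SAP 15.2.2:

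1. Define a numeric flag: `ready = 1` if the investigator deemed the wound ready for closure, `ready = 0` if any of the listed censoring rules applies. Use the same flag for Kaplan-Meier, log-rank and Cox.
2. Change the left side of the example MODEL line to `time*ready(0)`.
3. Require the number of events in the Cox fit to equal the number of events that the section already reports.

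The cost is one flag definition, a one-token change in the example code and one programmed check. No protocol amendment or new data are needed.
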